## 9.0 Interruption or Discontinuation of Treatment

A genuine effort must be made to determine the reason(s) why a patient fails to return for the necessary visits or is discontinued from the trial. Information regarding the reason for not completing the trial will be recorded on the appropriate case report forms.

It will be documented whether or not each patient completed the clinical study. If for any patient study treatment or observations were discontinued the reason will be recorded on the appropriate case report form. Reasons that a patient may discontinue participation in a clinical study are considered to constitute one of the following:

1. adverse event(s)
2. abnormal laboratory value(s)
3. abnormal test procedure result(s)
4. unsatisfactory therapeutic effect
5. subject's condition no longer requires study drug
6. protocol violation
7. subject withdrew consent
8. lost to follow-up
9. administrative problems
10. Death.

Any patient who receives at least one dose of trial medication will be included in the safety analysis.

## **10.0 Toxicity Monitoring**

Toxicity will be assessed using the NCI Common Toxicity Criteria.

### **10.1 Adverse events**

Information about all adverse events, whether volunteered by the subject, discovered by investigator questioning, or detected through physical examination, laboratory test or other means, will be collected and recorded and followed as appropriate. An adverse event is any undesirable sign, symptom or medical condition occurring after starting study drug (or therapy) even if the event is not considered to be related to study drug (or therapy). Study drug (or therapy) includes the drug (or therapy) under evaluation, and any reference or placebo drug (or therapy) given during any phase of the trial.

- if it is unclear what study treatment includes, list all drug(s), other therapies, changes to existing therapy, diagnostic procedure, etc. that are specified by the protocol

Medical conditions/diseases present before starting study treatment are only considered adverse events if they worsen after starting study treatment (any procedures specified in the protocol). Adverse events occurring before starting study treatment but after signing the informed consent form are recorded. Abnormal laboratory values or test results constitute adverse events only if they induce clinical signs or symptoms or require therapy, and are recorded.

### **Serious adverse events**

Information about all serious adverse events will be collected and recorded on the Serious Adverse Event Report Form. To ensure patient safety each serious adverse event must also be reported to Novartis within 24 hours of learning of its occurrence. A serious adverse event is an undesirable sign, symptom or medical condition which:

1. is fatal or life-threatening
2. required or prolonged hospitalization
3. results in persistent or significant disability/incapacity
4. constitutes a congenital anomaly or a birth defect
5. are medically significant, may jeopardize the subject and may require medical or surgical intervention to prevent one of the outcomes listed above.

Events not considered to be serious adverse events are hospitalizations for the:

- routine treatment or monitoring of the studied indication, not associated with any deterioration in condition.
- treatment, which was elective or pre-planned, for a pre-existing condition that did not worsen
- treatment on an emergency, outpatient basis for an event not fulfilling any of the definitions of serious given above and not resulting in hospital admission.

Pregnancy, although not itself a serious adverse event, should also be reported on a serious adverse event form or pregnancy form and be followed up to determine outcome, including spontaneous or voluntary termination, details of birth, and the presence or absence of any birth defects or congenital abnormalities.

Any serious adverse event occurring in a patient after providing informed consent and until 4 weeks after stopping the trial must be reported. The period after discontinuing study drug may be extended if there is a strong suspicion that the drug has not yet been eliminated. All serious adverse events must also be reported for the period in which the study protocol interferes with the standard medical treatment given to a patient (e.g. treatment withdrawal during washout period, change in treatment to a fixed dose of

concomitant medication).

## **10.2 Adverse Drug Reaction Reporting**

- 10.2.1 All adverse experiences occurring after administration of the first dose of study medication and on or before the final visit, will be reported on the Adverse Experience form in the patient's CRF.
- 7.2.1 At each visit/assessment, adverse experiences will be evaluated by the Investigator. Adverse experiences not previously documented in the study will be recorded in the adverse experience record form within the patient's CRF. The nature of each experience, date and time (where appropriate) of onset, outcome, course (i.e. intermittent or constant), maximum intensity, action taken with respect to dosage and relationship to treatment will be established. Details of changes to the dosage schedule or any corrective treatment will be recorded on the appropriate pages of the CRF.
- 7.2.3 Any serious adverse experiences which occur at any time during the clinical study or within 30 days of receiving the last dose of study medication, whether or not related to the study drug, will be reported immediately to the UT MD Anderson Cancer Center Institutional Review Board

## **10.3 Instructions for rapid notification of serious adverse events**

### **Reporting responsibility**

Each serious adverse event (but not pregnancies) must be reported by the investigator to Novartis within 24 hours of learning of its occurrence, even if it is not felt to be treatment-related. Follow-up information about a previously reported serious adverse event must also be reported to Novartis within 24 hours of receiving it. If the serious adverse event has not been previously documented (new occurrence) and it is thought to be related to study drug (or therapy), the Medical Safety Expert of the Clinical Safety & Epidemiology (CS&E) Department may contact the investigator to obtain further information. If warranted, an investigator alert may be issued, to inform all investigators involved in any study with the same drug (or therapy) that this serious adverse event has been reported.

### **Reporting procedures**

The investigator must complete the Serious Adverse Event Report Form in English, assess the relationship to study treatment and send the completed form by [contact]** within 24 hours to the local Novartis Clinical Safety & Epidemiology (CS&E) Department ensuring that the form is accurately and fully completed, must then fax it to Novartis CS&E Department within 2 to 3 calendar days for deaths or life-threatening events and 5 calendar days for other serious adverse events. The original and the duplicate copies of the Serious Adverse Event Form, and the fax confirmation sheet must be kept with the case report forms at the study site.

Follow-up information should describe whether the event has resolved or continues, if and how it was treated, whether the blind was broken or not, and whether the patient continued or discontinued study participation. The form and fax confirmation sheet must be retained. Pregnancy follow-up should describe the outcome of the pregnancy, including any voluntary or spontaneous termination, details of the birth, and the presence or absence of any congenital abnormalities or birth defects.

## **11.0 Patient Withdrawal From Study**

- 11.1 Evidence of disease progression
- 11.2 Development of a DLT that does not resolve within 2 weeks of stopping therapy.

- 11.3 Intercurrent illness which prevents further therapy  
General or specific changes in the patients condition which render the patient unacceptable for further treatment in the judgment of the investigator.
- 11.4 Protocol violation (including non-compliance).  
The patient or physician are free to discontinue treatment at any time if it is believed to be in the best interest of the patient.

## **12.0 Administrative Procedures**

### **12.1 Changes to the protocol**

Any change or addition to this protocol requires a written protocol amendment that must be approved by Novartis and the investigator before implementation. Amendments significantly affecting the safety of subjects, the scope of the investigation or the scientific quality of the study, require additional approval by the IRB/IEC/REB. A copy of the written approval of the IRB/IEC/REB, must be sent to Novartis

Amendments affecting only administrative aspects of the study do not require formal protocol amendments or IRB/IEC/REB approval but the IRB/IEC/REB of each center must be kept informed of such administrative changes. Examples of administrative changes not requiring formal protocol amendments and IRB/IEC/REB approval that can be treated as administrative amendments include:

1. changes in the staff used to monitor trials

### **12.2 Discontinuation of study**

Novartis reserves the right to discontinue support for any study under the conditions specified in the clinical trial agreement.

### **12.3 Ethics and Good Clinical Practice**

This study must be carried out in compliance with the protocol and Good Clinical Practice, as described in:

1. ICH Harmonized Tripartite Guidelines for Good Clinical Practice 1996.
2. Directive 91/507/EEC, The Rules Governing Medicinal Products in the European Community.
3. US 21 Code of Federal Regulations dealing with clinical studies (including parts 50 and 56 concerning informed consent and IRB regulations).
4. Declaration of Helsinki, concerning medical research in humans (Recommendations Guiding Physicians in Biomedical Research Involving Human Subjects, Helsinki 1964, amended Tokyo 1975, Venice 1983, Hong Kong 1989, Somerset West 1996).

The investigator agrees, when signing the protocol, to adhere to the instructions and procedures described in it and thereby to adhere to the principles of Good Clinical Practice that it conforms to.

### **12.4 Institutional Review Board/Independent Ethics Committee**

Before implementing this study, the protocol, the proposed informed consent form and other information to subjects, must be reviewed by a properly constituted Institutional Review Board/Independent Ethics Committee (IRB/IEC/REB). A signed and dated statement that the protocol and informed consent have been approved by the IRB/IEC/REB must be given to Novartis before study initiation. The name and occupation of the chairman and the members of the IRB/IEC/REB must be supplied to Novartis. Any amendments to the protocol, other than administrative ones, must be approved by this committee.

### **12.5 Informed consent**

The investigator must explain to each subject (or legally authorized representative) the nature of the study, its purpose, the procedures involved, the expected duration, the potential risks and benefits involved and any discomfort it may entail. Each subject must be informed that participation in the study is voluntary and that he/she may withdraw from the study at any time and that withdrawal of consent will not affect his/her subsequent medical treatment or relationship with the treating physician.

This informed consent should be given by means of a standard written statement, written in non-technical language. The subject should read and consider the statement before signing and dating it, and should be given a copy of the signed document. If the subject cannot read or sign the documents, oral presentation may be made or signature given by the subject's legally appointed representative, if witnessed by a person not involved in the study, mentioning that the patient could not read or sign the documents. No patient can enter the study before his/her informed consent has been obtained.

The informed consent form is considered to be part of the protocol, and must be submitted by the investigator with it for IRB/IEC/REB approval.

## 13.0 Statistical Methods

The major trial objective is to assess the efficacy of a regimen, which adds Imatinib Mesylate to Letrozole for the first-line treatment of metastatic breast cancer. A maximum of 45 patients will be accrued at MDACC at an expected rate of 2 patients per month, taking into consideration recent historical experience for this category of patients. The accrual period should thus be completed within 24 months. The maximum sample size of 45 patients will provide an estimate of ORR with 90% credibility interval (assuming targeted rate of 40%) of width 0.24. The final analysis will also report a summary of time to disease progression, any toxicities observed during treatment, and separate estimates of objective response rate (ORR) by type and extent of prior chemotherapy. All patients who receive any dose of therapy will be included in assessments of all outcomes, with patients removed from trial for any reason counted as failures in computing ORR.

Further investigation of Imatinib Mesylate is warranted only if its addition can substantially improve the efficacy of Letrozole alone. In a large randomized trial, single-agent Letrozole resulted in objective responses in 136 of 453 patients (30%). The trial will be monitored using a Bayesian method and with cohorts of size 15; termination will be recommended if there is strong evidence that ORR is unlikely to be more than 10% greater than with Letrozole alone. (Formally, the trial will be terminated after 15 or 30 patients if  $\Pr[\text{ORR (Letrozole + Imatinib Mesylate)} > \text{ORR (Letrozole)} + .10 \text{ data}] < 0.05$ . The comparative response rate for Letrozole alone is represented by a distribution of beta (136, 317), and a beta (0.60, 1.40) prior distribution is assumed for ORR of the experimental group. Maximum sample size is set at 45 patients.)

The first interim analysis will be conducted after the initial 15 patients have been evaluated for response. The trial will continue to accrue another 15 patients if at least 4 responses have been observed. At the second interim analysis, the trial will continue to accrue to the maximum sample size only if at least 8 objective responses have been observed among 30 patients.

A simulation study evaluated the properties of these stopping rules under several possible scenarios:

True ORR rate	Probability of early termination
.20	.83
.30	.40
.35	.22
.40	.11
.45	.05
.50	.02

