## Protocol Body

### 1.0 Objectives

1. To determine the efficacy of Letrozole plus Imatinib Mesylate in patients with ER and or PgR positive metastatic breast cancer. Efficacy will be measured by the rate of clinical tumor response.
2. To determine the safety and tolerability of Letrozole plus Imatinib Mesylate in patients with metastatic breast cancer.
3. To determine the time to disease progression and overall survival in patients with metastatic breast cancer who are treated with Letrozole plus Imatinib Mesylate.

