A recent study demonstrated that Letrozole induces high response rates in breast cancer patients, especially in those tumors which express higher levels of the tyrosine kinase receptors (Erb-B1 (EGFR) and Erb-B2 (Her-2/neu)). Preclinical studies have shown that hormone-resistant MCF-7 breast cancer cells with up-regulated tyrosine kinase signaling, had maximal growth inhibition and significantly delayed time to disease progression when they were treated with tyrosine kinase inhibitors in combination with antiestrogen agents. Therefore blockage of the estrogenic activity pathway and the tyrosine kinase pathway might not only have additive effects, but might also, by overcoming hormonal resistance caused by tyrosine kinase activity, synergistic effects. The aim of this study is to evaluate the efficacy and safety of Imatinib Mesylate in combination with Letrozole in patients with ER and /or PgR positive and C-kit and/or PDGFR positive metastatic breast cancer.

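### Does the lack of a decision cut-off at 45 patients leave the plan's condition for further investigation without an answer?

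*Combined protocol and SAP*

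**What the plan says.** All the relevant text is in Section 13.0, apart from the objective.

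- Condition for further work: "Further investigation of Imatinib Mesylate is warranted only if its addition can substantially improve the efficacy of Letrozole alone". That sentence carries no number. The text that follows gives the letrozole reference, 136 of 453 (30%).
- Monitoring: "termination will be recommended if there is strong evidence that ORR is unlikely to be more than 10% greater than with Letrozole alone". The formal rule begins "Formally, the trial will be terminated after 15 or 30 patients if" and requires the posterior probability that the combination's response rate exceeds letrozole's by more than .10 to be under 0.05. Letrozole is represented by beta(136, 317), and the combination has a beta(0.60, 1.40) prior. Accrual continues with at least 4/15 and at least 8/30 responses.
- At 45 patients: "an estimate of ORR with 90% credibility interval (assuming targeted rate of 40%) of width 0.24".
- Other final content: "The final analysis will also report a summary of time to disease progression, any toxicities observed during treatment, and separate estimates" of response rate by prior chemotherapy.

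Section 1.0 adds only that "Efficacy will be measured by the rate of clinical tumor response". The simulation table reports the probability of early termination and nothing about the result at 45.

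**The concern.** The section sets a comparative condition and builds the means to judge it, yet mentions the comparison only at the two interim looks. Passing those looks cannot stand in for a substantial improvement: with a true rate of 0.30, which is no improvement at all, 0.607 of trials still reach 45 patients.

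Two consequences seem to follow. A completed trial could meet the plan's own futility criterion without the plan saying so. And a result exactly on the 40% target, 18/45, could be read either way: better than letrozole with probability 0.903, but better by more than .10 with probability only 0.469. If the reading were chosen after the data were seen, the chance of a favourable conclusion would depend on that choice.

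**Working it through.** **Inputs (Section 13.0).** Letrozole p_L ~ beta(136, 317); combination prior beta(0.60, 1.40); margin .10; stopping level 0.05; continue with ≥4/15 and ≥8/30; maximum 45; target 40%. With x responses in n patients, p_E ~ beta(0.60 + x, 1.40 + n − x). The quantity of interest is Pr[p_E > p_L + .10], integrated over p_L.

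**1. The plan's own figures.**

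| Look | Result | Posterior probability | Action |
|---|---|---|---|
| 15 | 3 | 0.0431 | stop |
| 15 | 4 | 0.1217 | continue |
| 30 | 7 | 0.0259 | stop |
| 30 | 8 | 0.0594 | continue |

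Both printed boundaries are reproduced. Early termination is P(X1 ≤ 3) + Σ over x1 ≥ 4 of P(X1 = x1)·P(X2 ≤ 7 − x1), with X1 and X2 each binomial(15, p):

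| True rate | .20 | .30 | .35 | .40 | .45 | .50 |
|---|---|---|---|---|---|---|
| Exact | .819 | .393 | .220 | .108 | .048 | .019 |
| Printed | .83 | .40 | .22 | .11 | .05 | .02 |

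The 90% interval width at 18/45 is 0.514 − 0.282 = 0.232 with the stated prior, 0.238 from beta(18, 27) and 0.240 by the Wald formula 2 × 1.645 × √(0.4 × 0.6/45). The printed width is 0.24.

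**2. The same posterior at 45, with the interval the plan already reports (equal-tailed).**

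| Responses | Pr[> letrozole] | Pr[> letrozole + .10] | 90% interval |
|---|---|---|---|
| 12 | 0.3067 | 0.0315 | 0.169–0.379 |
| 13 | 0.4233 | 0.0602 | 0.187–0.402 |
| 18 | 0.9034 | 0.4690 | 0.282–0.514 |
| 19 | 0.9441 | 0.5830 | 0.302–0.536 |

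The upper limit of an equal-tailed 90% interval is the 95th posterior percentile. It falls below 0.40 exactly when Pr[p_E > 0.40] is under 0.05. That is the plan's futility rule with letrozole fixed at 30%, so both switch between 12 and 13 responses. The plan does not name the interval type. With a highest-density interval (the shortest 90% range of beta(13.6, 33.4)), the upper limit at 13/45 is 0.396, so the switch moves by one count.

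**3. How often a completed trial falls in the futile range.** P(reach 45 with ≤12 responses) is 0.1105 at a true rate of 0.20, 0.1075 at 0.30 and 0.0166 at 0.40. At 12/45 the observed rate is 12/45 = 26.7%, below letrozole's 30%.

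**4. How much the reading of success matters.** Probabilities include the interim looks.

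| Reading | .30 | .40 | .50 |
|---|---|---|---|
| ≥18/45 (observed rate at target) | 0.095 | 0.543 | 0.923 |
| ≥19/45 (equal-tailed interval above 30%) | 0.054 | 0.428 | 0.877 |
| ≥20/45 (highest-density interval above 30%) | 0.028 | 0.318 | 0.810 |

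The first two rows differ only at 18/45, which has probability 0.041 at 0.30 and 0.114 at 0.40. The third row arises because the highest-density lower limit at 19/45 is 0.2995, which is 0.0005 short of 0.30. None of the three readings is a criterion in the plan.

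**The case for a change.** The strongest case for a change is that the section itself makes further work conditional on a comparison, so it should say how that comparison is read once accrual is complete. Stating the reading beforehand removes the temptation to choose it afterwards. At 18/45 the calculation alone does not settle the matter. Between 13 and 17 responses, which has probability 0.404 at a true rate of 0.30 and 0.333 at 0.40, the plan is silent. A few added sentences would touch no patient, visit or interim rule.

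Part of this stands: no cut-off at 45 is written anywhere, and nothing says that the posterior probability will be reported there. The rest is weaker. The final-analysis list is introduced as additional to the response-rate estimate, so leaving the comparison out of it does not rule the comparison out. All 45 patients enter an estimate that the section sets beside 30% and 40%.

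The obvious rule also has costs. Calling ≥18/45 sufficient would declare success where the probability of clearing the margin is 0.469 and the interval includes 30%. It would turn a necessary condition into a sufficient one on response rate alone, although safety and time to progression are also objectives. And it would still leave 13 to 17 responses undecided.

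**Conclusion.** No change follows. This is a missing detail that an analyst can fill from the same section, and following the plan as written gives no wrong result. The boundaries are reproduced exactly, and the early-termination table and interval width to about 0.01. A single-arm phase II trial that stops for futility and ends with an estimate and interval is a legitimate design.

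The futile end is already covered by the planned output: at 12 or fewer responses the interval excludes the 40% target and the observed rate is below letrozole's. At the favourable end the plan leaves judgement to the sponsor, and the two main readings differ by one count. The wider spread of 0.318 to 0.543 at a true rate of 0.40 comes from readings supplied for this check, so it does not measure an error in the plan.

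These conclusions assume the stated priors and independent binomial responses with the interim rules followed. The exact match at 12 versus 13 responses also assumes an equal-tailed interval; another type could move it by one count. Reporting the posterior probability at 45 beside the interval would be natural in the final report and needs no amendment.

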## **3.0 Study Design**

This is a single-institution phase II study of once daily doses of Letrozole 2.5 mg and Imatinib Mesylate 400 mg administered orally twice a day in postmenopausal women with hormone-sensitive metastatic breast cancer. Even though no overlapping toxicity from the combination is expected, the starting dose for Imatinib Mesylate will be 300 mg twice a day for the first 3 patients and will be escalated up to 400mg twice a day within the same patient after 2 weeks. The dose of Letrozole will remain stable at 2.5 mg daily. If no toxicity occurs, subsequent patients will continue to start at 800 mg daily dose of Imatinib Mesylate as outlined in section 5.0.

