## **5.0 Treatment Plan**

### **5.1 Phase I Part**

The first 3 patients will be started at a dose of 300 mg Imatinib Mesylate twice a day and the dose will be escalated to 400 mg twice a day after 2 weeks in the same patient if no toxicity occurs. If grade 3/4 toxicity is observed, the dose of Imatinib Mesylate will be reduced as outlined in section 6.2 and 6.3 and the subsequent patients will be treated at that dose levels. The dose for Letrozole will be 2.5 mg, per oral, given once a day.

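### Safety is objective 2, but the only formal stopping rule counts responses, and no toxicity rate pauses accrual at any point

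*Combined protocol and SAP*

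**What the plan says.** Section 1.0 lists as its second objective "To determine the safety and tolerability of Letrozole plus Imatinib Mesylate in patients with metastatic breast cancer".

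Section 13.0 holds the only formal rule for ending the trial: "The trial will be monitored using a Bayesian method and with cohorts of size 15". It is worked out in response counts. At the first look, "The trial will continue to accrue another 15 patients if at least 4 responses have been observed"; at the second, at least 8 responses in 30 are needed to go on to 45. Toxicity enters that section as an item in the final report ("any toxicities observed during treatment") and indirectly through the handling of dropouts, "with patients removed from trial for any reason counted as failures in computing ORR".

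The provisions elsewhere are these:

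- **Run-in (3.0, 5.1).** Three patients start at 600 mg imatinib daily, and "the dose will be escalated to 400 mg twice a day after 2 weeks in the same patient if no toxicity occurs". Grade 3/4 toxicity lowers the dose for later patients. Otherwise, "If no toxicity occurs, subsequent patients will continue to start at 800 mg daily dose of Imatinib Mesylate". The grade meant by no toxicity is not stated.
- **Individual patients (5.3, 6.2, 6.3, 11.2).** There are holds and reductions, an end to treatment for unacceptable adverse events, and withdrawal for a DLT that has not resolved within 2 weeks. DLT is not defined.
- **Reporting (10.1 to 10.3).** Serious events go to the supporting company within 24 hours and to the IRB immediately. An investigator alert may follow.
- **Contract (12.2).** The company may end its support under the trial agreement.

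None of these gives a toxicity rate, count or posterior probability that acts on accrual.

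**The concern.** A response rule sees toxicity only when toxicity removes patients. If grade 3/4 events are common but handled by holds and reductions, and the regimen is active, the stated rule carries the trial on towards 45 patients. The plan's own background makes that pattern plausible. In the leukemia studies summarised in section 6.0, 2% to 5% of patients stopped drug for adverse events, while 25% to 40% needed temporary interruptions.

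The prior evidence is reassuring but indirect. Section 3.0 states that "no overlapping toxicity from the combination is expected". Section 6.0 found no obvious difference between 400 and 600 mg in leukemia apart from grade 1/2 edema, but says the comparison is confounded by dose escalation and by analysis according to starting dose. Table 5 gives related grade 3/4 events in 21% and 22% of GIST patients at 400 and 600 mg. No toxicity rate is given for 800 mg daily or for the combination. What is at stake is how many patients are treated before an excess triggers a pre-agreed review.

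**Working it through.** **1. Reproduce the plan's response rule.** Inputs from section 13.0: looks at 15 and 30, beta(0.60, 1.40) prior, beta(136, 317) for letrozole, margin 0.10, stop if the posterior probability is below 0.05. That probability is 0.043 at 3/15 and 0.122 at 4/15, then 0.026 at 7/30 and 0.059 at 8/30, so the printed boundaries follow. Early termination is Pr(X15 ≤ 3) + Pr(X15 ≥ 4 and X30 ≤ 7).

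| True ORR | 0.20 | 0.30 | 0.35 | 0.40 | 0.45 | 0.50 |
|---|---|---|---|---|---|---|
| Plan | .83 | .40 | .22 | .11 | .05 | .02 |
| Exact | .819 | .393 | .220 | .108 | .048 | .019 |

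The rule is correctly calculated for response.

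**2. How much toxicity the response rule can see.** Suppose a share r is removed before, and independently of, response. The effective ORR is then 0.50 × (1 − r). For r = 0%, 20%, 30% and 50% it is 0.50, 0.40, 0.35 and 0.25, and early termination is 0.02, 0.11, 0.22 and 0.61. Managed toxicity corresponds to r near zero.

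**3. What the run-in can see.** The chance of no grade 3/4 event in 3 patients is (1 − p)³: 34%, 22% and 12.5% at p = 0.30, 0.40 and 0.50. After 0/3 the one-sided 95% upper limit is 1 − 0.05^(1/3) = 63%. If any grade of toxicity blocks escalation, the chance of reaching 800 mg is lower.

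**4. An illustrative toxicity rule.** The limit of 0.30 and the cut-off of 0.95 are assumptions; the documents give neither. The boundary is the smallest x with Pr(Beta(a + x, b + n − x) > 0.30) > 0.95.

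| Prior | 7/15 | 8/15 | 13/30 | 14/30 |
|---|---|---|---|---|
| beta(0.6, 1.4) | 0.893 | 0.960 | 0.929 | 0.967 |
| beta(0.5, 0.5) | 0.917 | 0.972 | 0.941 | 0.974 |
| beta(1, 1) | 0.926 | 0.974 | 0.947 | 0.976 |

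All three priors give 8/15 and 14/30.

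**5. Operating characteristics.** Let R1 and R2 be the chances of passing the first response look and both response looks, and T1 and T2 the same for toxicity. With response and toxicity independent, and treating a pause as final, E[N] = 15 + 15·R1·T1 + 15·R2·T2. At ORR 0.50, R1 = 0.982 and R2 = 0.981, so the response rule alone gives 15 + 14.74 + 14.72 ≈ 44.5. At toxicity 0.50, T1 = 0.500 and T2 = 0.252, so E[N] = 15 + 7.37 + 3.71 ≈ 26.1.

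| True grade 3/4 rate | 0.20 | 0.30 | 0.40 | 0.50 |
|---|---|---|---|---|
| Pause probability | 0.5% | 7% | 35% | 75% |
| E[N] with both rules, ORR 0.50 | 44.3 | 42.7 | 36.2 | 26.1 |

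At 0.22, the Table 5 rate for 600 mg, the pause probability is 0.9%.

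**6. Sensitivity to the limit (cut-off 0.95).** Limit 0.25 gives 7/15 and 12/30, pausing 8% at 0.25, 62% at 0.40 and 92% at 0.50. Limit 0.35 gives 9/15 and, depending on the prior, 15/30 or 16/30, pausing 6–9% at 0.35, 15–21% at 0.40 and 49–60% at 0.50.

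**7. Timing.** Fifteen patients at 2 per month take 7.5 months. The response look also needs restaging at month 2 (section 7.1) and confirmation 4 weeks later (section 8.3). For a last-enrolled responder that is 7.5 + 2 + 1 ≈ 10.5 months, so the first look falls at roughly 10 months or later. Section 13.0 does not say whether accrual waits.

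**The case against.** The strongest reply is that this is an optional rule left out, not an error. Section 13.0 calls efficacy the major objective, and a final toxicity summary in all treated patients can answer objective 2. That is correct: nothing in the plan is contradictory or miscalculated here.

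The second reply is that the safeguards are denser than the missing rule suggests. Even grade 2 non-hematologic toxicity forces a hold, and recurrence forces a reduction (6.2). Laboratory tests run through the first 8 weeks (7.1), adverse events are assessed at every visit (10.2), and removals feed the response rule. This narrows the gap to managed toxicity in an active regimen but does not close it.

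The third concerns size. A reader might infer from 44.5 against 26.1 that the plan would needlessly expose about 18 patients. The documents do not support that. At a true rate of 0.50 the run-in shows at least one grade 3/4 event 87.5% of the time (1 − 0.125), and section 5.1 then lowers the dose for later patients. A pause for review need not end accrual. And 0.50 is more than twice the only overall related grade 3/4 rate given at 600 mg (22%). This objection stands, so the E[N] differences are upper bounds.

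A reader might also infer that the trial cannot be stopped for safety, or that the run-in can halt accrual. Neither follows: nothing bars a safety stop, and the run-in only changes dose.

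Finally, 8/15 means 53% observed toxicity, and at a true rate of 0.40 the first look fires only 21% of the time. That also stands: the rule is a backstop.

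**Conclusion.** The point holds as a gap in design. No toxicity rate pauses accrual at any stage, including the run-in, and grade 3/4 toxicity that is managed without removing patients is invisible to the one formal rule. The plan supplies no toxicity rate for 800 mg daily with letrozole that would make the gap harmless.

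The size depends on an unknown rate. At ORR 0.50, the most the illustrative rule could save is 0.2 patients at a true rate of 0.20 (44.5 − 44.3), 1.8 at 0.30, 8.3 at 0.40 and 18.4 at 0.50. These figures assume the 0.30 limit and 0.95 cut-off, toxicity independent of response, no dose cut from the run-in, and every pause ending accrual. The absence of the rule is certain; how much it matters is moderately uncertain. It should be added because it is cheap, not because the documents show that the regimen is unsafe.

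**What to change.** Add one paragraph and one table to section 13.0:

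- **Endpoint.** The proportion of treated patients with grade 3/4 treatment-related toxicity. List the events that count, for example neutropenia and thrombocytopenia as defined in 6.3, and say explicitly whether anemia counts, since 6.3 makes no dose reduction for it.
- **Rule.** Pause accrual for review or dose reduction if Pr(rate > limit | data) > 0.95. The investigator and sponsor set the limit and prior.
- **Timing.** Apply it when 15 and then 30 patients have completed a fixed early window, for example 8 weeks, so that it does not wait for confirmed response. At the planned accrual the first look would come at about 7.5 + 2 = 9.5 months, roughly one month sooner than a look that waits for confirmation. State whether accrual continues meanwhile.
- **Table.** Print the boundaries and operating characteristics beside the response table.

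In the same edit, define DLT in 11.2 and state the grade meant by no toxicity in 3.0 and 5.1. Keep the run-in, withdrawal rules and serious-event reporting.

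The cost is small, since toxicity grades and relationship to treatment are already collected. The price is about a 7% chance of an unneeded pause when the true rate equals the assumed 0.30 limit. A 0.90 cut-off raises that to 11–16%, depending on the prior. Power at a true rate of 0.40 is only 35%, so the rule supplements serious-event review and does not replace it.
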